Study Description	The focus of this proposal is on expanding access to voluntary smoke-free homes to formerly homeless residents residing in permanent supportive housing, and examining the impact of this intervention on reducing tobacco-caused disparities. In this study, we will conduct a multi-site, community-based cluster-randomized wait-list controlled trial of our multi-faceted smoke-free home intervention among 400 permanent supportive housing residents residing in 20 permanent supportive housing sites across the San Francisco Bay Area with the goal of increasing voluntary adoption of smoke-free homes. Our specific aims are: Aim 1: Conduct a cluster randomized trial to estimate the effect of our smoke-free home intervention on residents' voluntary adoption of smoke-free homes. Aim 2: Evaluate the cost-effectiveness of the smoke-free home intervention. Aim 3: Determine characteristics of high and low adopters at the individual level, and social and environmental barriers and enablers of adoption, scalability and sustainability of the intervention.
Study Intervention	The multi-faceted intervention, delivered by study staff includes: 1) one-on-one counseling to permanent supportive housing residents who are smokers on how to adopt a smoke-free home, and 2) training for permanent supportive housing staff on how to provide referrals to cessation services.
Study Population	The proposed study will include all adult participants across the lifespan, without any restrictions based on age, gender or race/ethnicity. Eligible participants will include those who are ≥ 18 years of age. However, no children under the age of 18 years of age will be included in this study of adult cigarette smokers. While PSH residents who participate in the smoke-free home intervention study might have children living with them in their home, the unit of analysis will be the residents and not their children. However, we will gather information both quantitatively and qualitatively on whether children live in their homes, and the influence, if any, that children had on residents' adoption of a voluntary smoke-free home.
Primary Objective	The primary outcome is self-reported voluntary adoption of smoke-free homes for ≥ 90 days at 6 months follow-up.

Secondary Objectives	The secondary outcome is 7-day point prevalence abstinence at 6 months follow-up, measured as self-report of abstinence at the 6-month follow-up and an expired carbon monoxide of ≤ 5 parts per million (ppm) as abstinence
Recruitment Methods	
We will recruit 400 PSH resident participants, with 200 each in the intervention and wait-list control arms (~20 participants per site; Figure 6, Table in Recruitment and retention section in human subjects). Within each site, all resident participants will be informed about the study and invited to participate. We will recruit participants within blocks of four housing sites per month, with each block containing two intervention and two wait-list control sites, and anticipating roll-out of one such block per month. We anticipate completing recruitment and enrollment of all participants in 6 months, allowing for a one-to-two-month extension to complete these activities. We will offer the intervention to the wait-list control participants once all participants in the intervention sites from the same block have completed their 6-month follow-up.
 
We will recruit 400 resident participants, with 200 participants each in the intervention and wait-list control arms (~20 participants per site). Within each site, study staff will advertise the study to residents the week prior to enrollment by placing flyers at the study site and making announcements at community meetings. After the informational meeting, study staff will be present at the recruitment sites during designated times to screen interested participants for eligibility and enroll those eligible into the study. We have used these study procedures successfully in our pilot study.
 
All staff participants will be recruited at the time of the resident intervention, via email. PSH staff in intervention sites will receive the intervention at the same time as residents in those sites; those in wait-list control sites will receive the intervention once intervention site participants have completed their follow-up assessments. Staff who agree to enroll will be provided information about the study at the time of enrollment, and will complete a written informed consent prior to the training.

Sample Size	We plan to recruit 400 resident participants and 100 staff participants.

1.1 Background on condition, symptom, behavior, or other primary study focus

The proposed study focuses on cancer healthy equity by examining the impact of a brief intervention to increase voluntary adoption of smoke-free homes among formerly homeless adults living in permanent supportive housing (PSH). PSH is subsidized housing with closely linked or on-site voluntary medical and/or social services for individuals with a history of chronic homelessness.^{1,2} In 2017, over 370,000 formerly homeless individuals lived in PSH in the US.³ Housing First, the most common approach, uses a harm reduction framework and provides housing without preconditions of abstinence from alcohol or substance use or a requirement to engage in supportive services prior to obtaining housing or to maintain housing.¹

Social determinants of health are associated with high rates of tobacco use among people who experience homelessness.⁴ These determinants include extreme poverty and the social marginalization that results from being homeless, increased availability of tobacco products in low-income communities, and limited access to cessation resources and smoke-free housing.^{4,5} Approximately 50% of those living in PSH report current smoking.⁶ Mortality rates among PSH residents are at least double that of age-matched individuals in the general population⁷ and tobacco-caused chronic diseases including cancers and cardiovascular disease contribute to over 60% of the all-cause mortality of PSH dwelling individuals.⁷

Tobacco use also incurs a substantial financial burden. In prior work with PSH residents in the San Francisco Bay Area, we found that residents who smoked spent 12% (median, range 5%-26%) of their monthly income on tobacco.⁸ This interfered with residents' ability to pay rent, putting them at risk of eviction.⁹ Residents reported prioritizing tobacco purchases over food purchases, increasing risk for food insecurity.¹⁰

Despite high rates of tobacco use and its detrimental impact on PSH residents' health and financial well-being,¹⁰ PSH typically do not have mandated smoke-free policies restricting indoor smoking in living areas nor do they offer smoking cessation services.⁹ Smoke-free policies and smoking cessation services are among the most effective tobacco control interventions. The Department of Housing and Urban Development (HUD)-managed public housing authority housing has a mandated smoke-free policy and, in most HUD sites, that mandate is accompanied with access to cessation resources.^{11,12} In contrast, smoke-free policies are uncommon in PSH and most PSH are not equipped to offer cessation services.^{9,13}

1.2 Background on study intervention

There are several approaches to implementing smoke-free policies in housing such as having a city ordinance restricting smoking in multi-unit housing or housing providers mandating smoke-free policies on their properties. However, these approaches may be difficult to implement in PSH for several reasons. First, there is concern that mandated policies conflict with PSH's harm reduction framework,⁹ potentially increasing risk of unsheltered homelessness if people left PSH because of the policy or were evicted because of a policy violation. Second, PSH staff may lack resources and time to enforce a smoke-free policy even if they put one into effect.⁹ However, in the absence of smoke-free policies, PSH residents are unprotected from secondhand smoke exposure unless they voluntarily adopted smoke-free homes. Thus, research is needed to: (a) determine whether individually-directed strategies are effective in

increasing voluntary adoption of smoke-free homes among PSH residents, and (b) determine whether these strategies can be brought to scale within PSH.

In our previous pilot study, we conducted a single-arm trial of an intervention to increase voluntary adoption of smoke-free homes, i.e., a voluntary no-smoking rule in one's home, among 100 formerly homeless adults in PSH.¹⁴ The multi-faceted voluntary smoke-free home intervention acted upon the individual, social and organizational levels to modify tobacco use behavior. The intervention consisted of providing a step-by-step guide to residents on how to voluntarily adopt a smoke-free home as well as training PSH staff on how to refer residents to local cessation resources. At 6 months, 31% of residents adopted a voluntary smoke-free home compared to 12% at baseline.

1.3 Study Rationale

In this study, we will conduct a multi-site, community-based cluster-randomized wait-list controlled trial of our multi-faceted smoke-free home intervention among 400 PSH residents residing in 20 PSH sites across the San Francisco Bay Area.

This proposal is **significant** because it is aimed at mitigating some of the structural inequities that have led to an increase in tobacco-caused cancer disparities in this population. The intervention delivered by study staff includes providing PSH residents the tools to voluntarily adopt a smoke-free home, and training PSH staff to offer referrals to cessation services to residents. By influencing tobacco use behavior at the individual-level, the intervention may have the primary effect of increasing voluntary adoption of a smoke-free home and may also have the secondary effect of increasing smoking cessation. This has the potential to reduce the incidence of tobacco-caused diseases, including cancers.

1.4 Risk/Benefit Assessment

Potential risks: There may be a potential for loss of privacy relating to the information asked in the questionnaires, particularly around issues on mental health disorders, substance use disorders, and previous history of homelessness. Loss of privacy or confidentiality— particularly around mental health, illicit substance use, HIV status, impaired function, and information contained in medical records – could result in embarrassment or social marginalization. In the case of illicit substance use, loss of privacy or confidentiality could result in legal consequences. Because we will ask participants to consent to keep on file their name and contact and tracking information, there may be a potential for loss of confidentiality. Participants may experience symptoms of nicotine withdrawal from reducing consumption or quitting smoking. These symptoms may include irritability, fatigue, headaches or cravings for cigarettes. Participants may also experience hunger as a result of reducing consumption or quitting smoking. There is a low risk of study participants experiencing fatigue and/or boredom during study visits. In addition to the above, we note other risks that may be relevant to our study population. Given the significantly low economic status of our study participants, study incentives may be coercive. We believe that the risk of these events is low given the measures we will put in place to minimize these risks (see below).

Adequacy of protection against risks

1) Procedures for protecting against loss of privacy. Although we collect basic information from PSH resident and staff participants on socio-demographics and factors that can influence smoking cessation such as mental health disorders or substance use disorders, it will be kept to

a minimum to minimize any psychological risk. All interviews will be conducted in a way that is formative without breaching the confidentiality of individuals participating in the study. We will ensure participants that responses to the questionnaires, in-depth, semi-structured interviews or focus groups will not affect their eligibility for receiving services. We will assure participants who decide not to participate that their decision would not affect their ability to seek services.

Participation in this study is voluntary.

2) Procedures for protecting against loss of confidentiality. There is a potential for loss of confidentiality, however we will take measures to minimize this risk. Each participant will have a unique alpha-numeric identification (ID) number. We will use the UCSF REDCap secure database to enter personal identifying information and to create questionnaires for each of the studies. Identifying information collected from participants for tracking purposes will be stored separately from research data and will not be associated with the participants' unique study ID number. All questionnaire data will be entered in real-time using an iPad through a secure VPN network. In-depth, semi-structured interviews and focus groups will be audio-recorded. These recordings and their transcriptions will be stored on our secure server at UCSF. The server where data will be stored is backed up nightly. We will periodically go through the study data to make sure there is no personal identifying information. Only study staff will have access to study data. For added protection of confidentiality, we will apply for a Certificate of Confidentiality from the National Cancer Institute.

3) Procedures for protection against legal risk to participants. The questionnaires will include questions about illegal behavior (e.g. the use of illicit drugs). Procedures explained above for protecting privacy of individuals and confidentiality of data will minimize the legal risk to participants. For added protection of confidentiality of data, we will apply for a Certificate of Confidentiality from the National Cancer Institute. Trained study staff will inform participants of legal risks during the informed consent process and will explain that participants can skip out of any interview questions they are not comfortable answering.

4) Procedures for protecting against coercion. Reimbursements may be coercive. There is controversy around whether reimbursements could be coercive or used to purchase illicit drugs when given to indigent populations participating in research. In trying to balance the need to reimburse participants for their time while limiting coercion and/or dangerous behaviors, we have set reimbursement levels comparable to those used in studies in similar populations.⁴⁵⁻⁴⁷ An alternative to cash reimbursements, we have chosen to reimburse in the form of gift certificates for grocery stores and general pharmacies.

5) Procedures for protecting against hunger. It is possible that individuals who are attempting to quit smoking may experience hunger. Should this issue arise during the intervention, we will provide resident participants a list of resources of free food including food banks for food in bulk, soup kitchens for daily meals, and other free meal programs.

6) Procedures for protecting against withdrawal symptoms. Participants may experience symptoms of nicotine withdrawal from reducing consumption or quitting smoking. These symptoms include irritability, fatigue, headaches or cravings for cigarettes. Participants who experience these symptoms will be referred to their primary care providers to obtain a prescription for nicotine replacement therapy or other medications for cessation and/or to be evaluated for contraindications to these medications. Study staff will ask participants about these symptoms during follow-up visits.

7) Procedures for handling reportable conditions. During the informed consent process, participants will be informed of information that must be reported by law should it be revealed during study visits, including suicidality and homicidality. The PI will train the study staff on how to assess for symptoms of suicidality or homicidality, and the procedures to follow in the event of these occurrences. In addition, the PI will be on call at all times and will be available for consultation.

- 8) Procedures for protecting against fatigue or boredom. The enrollment study visit will last approximately 1 hour, and the follow-up visits at 3- and 6 months (intervention and wait-list control participants) and 9- and 12-months (wait-list control participants) will last approximately a half-hour to 45 minutes. The in-depth, semi-structured interviews and focus group in Aim 3 will last 60 minutes to 90 minutes. Study staff will inform participants, during informed consent and at each study visit, that they can take breaks or stop participating in the study at any time.
- 9) Added protections for vulnerable populations. If a participant becomes incarcerated during the course of the study, they will be censored from participation during incarceration. If released from jail/prison during the study timeframe they can choose to re-enroll and a research assistant will repeat the informed consent process using procedures explained above.
- 10) Protections against COVID-19. We will ensure that all study procedures comply with protocols in place at PSH sites to minimize COVID-19. These procedure may include minimizing the number of days we are on-site to conduct recruitment, maintaining physical distancing protocols, incorporating a universal COVID-19 screen at each encounter, conducting follow-up visits by zoom or telephone, and conducting the staff training by zoom. For participants, who screen positive for COVID-19 symptoms, we will refer participants to their primary care provider/medical homes to get tested and evaluated. For participants who report other needs as a result of COVID-19 (e.g., food, social services), we will request permission to share this information with their case managers and also refer them to their medical homes to get additional support. Moreover, all staff will be required to wear personal protective equipment that is compliant with state guidelines. All participants will be required to wear a mask when interacting with staff and maintain at least 6 feet of physical distance.

2 Study Objectives and Endpoints

2.1 Primary Objective

Primary Objective	Endpoint(s)	Time Frame
1. Self-reported voluntary adoption of smoke-free homes for ≥90 days at 6 months follow-up.	
 The proportion of people who adopt a smoke-free home voluntarily 	6 months follow-up

2.2 Secondary Objective(s)

Secondary Objective	Endpoint(s)	Time Frame
1. 7-day point prevalence abstinence at 6 months follow-up, biochemically verified using CO ≤ 5 ppm as abstinence	
 The proportion of people who achieve abstinence at 6 months follow-up 	6 months follow-up

2.3 Exploratory Objective(s)

Exploratory Objective	Endpoint(s)
1. Behavioral outcomes for PSH staff include change in SKAP scores	Measured at baseline, 3 and 6 months follow-up
2. Air nicotine monitoring in a random sample of (~ 200 participants)	6 months follow-up

3 Study Design

3.1 Characteristics

Overview of the intervention. The intervention, delivered by study staff includes: 1) one-on-one counseling to PSH residents who are smokers on how to adopt a smoke-free home, and 2) training for PSH staff on how to provide referrals to cessation services.

Trial design. We have chosen a cluster-randomized, wait-list controlled trial,^{75,76} where PSH sites will be randomized into intervention and wait-list control groups. Those in the wait-list control group will receive usual care first and then cross over to the intervention arm.

Setting. Study procedures will take place in a private room at each PSH site.

Study procedures for PSH resident participants. Eligible resident participants include current smokers [(smoked at least 100 cigarettes in lifetime (i.e. the standard definition for a life-time smoker), daily or non-daily smoking in the past 7 days and at least 5 cigarettes per day, verified by expired Carbon Monoxide (CO) ≥ 8 parts per million (ppm)]⁷⁷ who smoke in their homes and

expect to live in the PSH site for at least 12 months, are ≥ 18 years of age, are English proficient, and are able to provide informed consent. Study staff will advertise the study to residents the week prior to enrollment by placing flyers at the site and making announcements at community meetings. Study staff will be present at the recruitment sites during designated times to screen interested participants for eligibility, obtain written informed consent using the teach-to-goal method,⁷⁸ and enroll those eligible. **The expired CO assessment for eligibility assessment is to ensure that participants recruited are regular smokers who smoke an average of 5 cigarettes per day. To obtain a CO assessment, the participant blows into a handheld CO monitor that records the expired CO reading (Bedfont EC50 Smokerlyser; Bedfont Scientific Ltd). We considered including monolingual Spanish speaking participants in our study, however, the proportion of monolingual Spanish speaking participants is ~ 5% based on estimates from our partner organizations where the study will be conducted. Therefore, we chose to include English speaking participants in this study.**

Study procedures for PSH staff participants. Eligible PSH staff participants include service staff (e.g., case managers), who are ≥ 18 years of age, are willing to engage in a 2-hour training, and are able to provide informed consent. Staff in each site will be contacted via email, and invited to participate in a 2-hour training. Study staff will screen PSH staff for eligibility, obtain written informed consent using the teach-to-goal method,⁷⁸ and offer dates for the training.

Randomization and allocation. We will randomize 20 PSH sites into intervention and waitlist control arms. We will use the method of restricted randomization—commonly applied in cluster-randomized trials with small numbers of clusters—to ensure an acceptable level of balance across groups at baseline.⁷⁶ First, we will create two sets of 10 housing sites balanced on preexisting variables describing relevant characteristics of sites and their residents, e.g., property size, current smoking-related policies, and geographic location. Second, we will randomly assign one set of sites to intervention and the other to the wait-list control.

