4.2 Recruitment Methods

Recruitment schedule. We will recruit 400 PSH resident participants, with 200 each in the intervention and wait-list control arms (~20 participants per site; Figure 6, Table in Recruitment and retainment section in human subjects). Within each site, all resident participants will be informed about the study and invited to participate. We will recruit participants within blocks of four housing sites per month, with each block containing two intervention and two wait-list control sites, and anticipating roll-out of one such block per month. We anticipate completing recruitment and enrollment of all participants in 6 months, allowing for a one-to-two-month extension to complete these activities. We will offer the intervention to the wait-list control participants once all participants in the intervention sites from the same block have completed their 6-month follow-up. We expect to enroll 100 PSH staff. We will obtain information on the total number of residents and staff at each site to provide an estimate of the proportion enrolled in the intervention.

Within each site, study staff will advertise the study to residents the week prior to enrollment by placing flyers at the study site and making announcements at community meetings. After the informational meeting, study staff will be present at the recruitment sites during designated times to screen interested participants for eligibility and enroll those eligible into the study. Study staff will describe the purpose of the study, the study procedures, including risks and benefits, and obtain written informed consent using the teach-to-goal method at the time of eligibility.⁷⁸ Participants will complete the baseline questionnaire and will receive the study staff-delivered intervention within one week of enrollment. We have adjusted the timeline for recruitment, intervention delivery and follow-up to account for extra time that we may need to complete study procedures to follow protocols around social distancing that PSH sites may have put in place due to COVID-19.

Data collection reimbursements. We will reimburse all resident participants with [REDACTED] gift cards for completing the baseline questionnaire, [REDACTED] the 3-month questionnaire and [REDACTED] the 6-

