9.1 Sample Size Considerations

9.1.1 Sample Size and Power Estimate

Our study is powered to assess both the primary outcome of smoke-free home adoption ≥ 90 days and the secondary outcome of point prevalence abstinence at 6-months follow-up. We designed the RCT to detect medium-large effect sizes, which are consistent with estimates from our pilot study¹⁴ and from other studies of brief interventions to increase adoption of smoke-free homes (intervention effect $\geq 40\%$ versus control effect $\sim 25\%$).^{32,139} Power analyses assumed 80% power; two-tailed alpha of 0.05; N=400 smoking residents recruited from 20 PSH units; 80% retention at 6-months; average 6-month site cluster size of 16 residents; group comparisons of 6-month binary outcomes describing adoption of a smoke-free home for ≥ 90 days and point prevalence abstinence from preliminary data, expected 6-month control group outcome rates of 12% and 4% for smoke-free home adoption and point prevalence abstinence, respectively; from preliminary data, intra-site outcome correlations of 0.077 (ρ_{SFH}) and zero (ρ_{PPA}); and mixed logistic models including random intercepts for sites. Estimated design effects equaled $1+(16-1)\rho_{SFH}=2.16$ and $1+(16-1)\rho_{PPA}=1.0$, respectively. For the primary outcome of voluntary smoke-free home adoption, the minimum detectable effect for the intervention group is 30.3% compared to 12% for the control group, which compares favorably with 31.3% obtained in our pilot study as well.¹⁴ For the secondary outcome of point prevalence abstinence at 6 months, the minimum detectable effect in the intervention group is 12.6% compared to 4% in the control group, which compares favorably with 16.9% obtained in the pilot study.¹⁴

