9.1.3 Stratification Factors

We will create two sets of 10 housing sites balanced on preexisting variables describing relevant characteristics of sites and their residents, e.g., property size, current smoking-related policies, and geographic location.

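### The allocation rule as written randomises only which of two pre-formed sets of 10 sites gets the intervention, so just two mirror-image allocations are possible

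*Combined protocol and SAP*

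**What the plan says.** Section 3.1 (Characteristics, paragraph on randomization and allocation) states the unit and the method: "We will randomize 20 PSH sites into intervention and waitlist control arms", and "We will use the method of restricted randomization". It then gives two steps.

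- Step one: "First, we will create two sets of 10 housing sites balanced on preexisting variables". Property size, smoking policy and location are offered as examples of such variables.
- Step two: "Second, we will randomly assign one set of sites to intervention and the other to the wait-list control".

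Section 9.1.3 (Stratification Factors) repeats step one only: "We will create two sets of 10 housing sites balanced on preexisting variables describing relevant characteristics of sites and their residents". Sections 4.6 and 9.1.2 refer back to 3.1. No section gives a final list of balancing variables, a numeric balance limit, a list of acceptable allocations, or a random draw of the split itself.

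Section 4.2 (Recruitment Methods) schedules recruitment in monthly blocks of four sites, "with each block containing two intervention and two wait-list control sites". It does not call these randomisation blocks.

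Section 9.3.2 plans mixed logistic models with random intercepts for sites and residents. It plans no permutation test.

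**The concern.** Restricted randomisation in a trial with few clusters ordinarily means setting balance limits, identifying the many allocations that meet them, and drawing one at random. The two steps in 3.1 contain one binary draw. Followed literally, they always put a given site in the same arm as the same nine others.

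This matters for what the comparison rests on. With many possible allocations, an unmeasured site characteristic is spread between the arms by chance. With two, the size of any such difference is fixed when the sets are formed, and the draw decides only which arm it favours. Balancing on measured variables does not remove this for characteristics unrelated to them. The propensity score adjustment in 9.3.2 applies only to factors found imbalanced at baseline, so it does not reach unmeasured site differences either. Nor could a permutation test be used to check the model-based result.

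**Working it through.** **The plan's own figure.** Inputs from 9.1.1: 160 residents analysed per arm (80% of 200), 16 per site, intra-site correlation 0.077, control rate 12%, 80% power, "two-tailed alpha of 0.05".

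- Design effect: 1 + (16 − 1) × 0.077 = 2.155 (the plan states 2.16).
- Effective number per arm: 160 / 2.155 = 74.2.
- At 30.3%, the unpooled standard error is √[(0.12 × 0.88 + 0.303 × 0.697) / 74.2] = 0.0653. Then 0.12 + (1.960 + 0.842) × 0.0653 = 0.303.

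The stated minimum detectable rate of 30.3% is reproduced. The sample-size arithmetic is not at fault; the point concerns allocation only.

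**Counting allocations.** Let M be the number of equally likely allocations. For a symmetric statistic, the smallest attainable permutation p-value is 1/M one-sided and 2/M two-sided.

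| Scheme | M | Smallest two-sided p |
|---|---|---|
| Section 3.1 as written | 2 | 2/2 = 1.0 |
| Two sites per arm in each of five pre-formed blocks of four | C(4,2)^5 = 6^5 = 7,776 | 0.00026 |
| Any 10 of 20 sites | C(20,10) = 184,756 | 0.00001 |

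The number of blocks is 20 / 4 = 5. Reaching a two-sided 0.05 needs 2/M ≤ 0.05, that is M ≥ 40. Balance limits reduce the last two rows. As an illustration only, if they kept 1% to 10% of the 184,756 allocations, about 1,848 to 18,476 would remain.

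**Type I error.** Null data were simulated with beta-binomial outcomes at a 12% rate, correlation 0.077, 10 sites per arm and 16 residents per site, using a site-level t test on 18 degrees of freedom as a simple stand-in for the mixed model.

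- Averaged over exchangeable site effects, type I error is about 5% for the two-set rule and for a 2:2 block draw.
- Conditional on one realised allocation, both designs give a median of 1.5% and a 95th percentile of 21.5%. The 99th percentile is about 43% for the fixed split and 42% for the block draw.

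The two designs therefore perform alike when site effects are exchangeable. They differ when the making of the sets is related to unmeasured site effects: drawing from many allocations protects against that, and a single binary draw does not. The simulation does not model balancing on covariates, which would narrow the spread to the extent that the covariates predict the outcome.

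**The case against.** The best defence is that the documents do not say how the sets are created. Drawing a balanced split at random and then assigning the labels is compatible with 3.1, given that it names restricted randomisation. This stands as a limit on the point: if that is the intention, what is missing is a sentence. As the text reads, however, no such draw is stated anywhere.

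It is also fair that the planned inference is model-based and no permutation test is proposed. That answers any claim that the primary analysis fails. It does not supply a design-based check.

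A reader might infer more than the documents support:

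- **That type I error is inflated compared with block randomisation.** This appears only if the spread for one fixed split (95th percentile about 22%) is set against block-design rates averaged over many allocations (about 2% to 8%). Compared like with like, the spreads are essentially the same.
- **That the rule creates a between-set imbalance with an SD of 4.0 points.** √(0.077 × 0.12 × 0.88) × √(2/10) = 0.040 holds for any unrestricted 10-versus-10 allocation of exchangeable sites, and this variance is already in the design effect.
- **That the mixed model assumes sites were independently allocated.** It assumes exchangeable site effects.
- **That the sets are chosen by hand.** The documents do not say so.
- **That the 2:2 recruitment blocks must be put together once allocation is known.** Blocks of two sites from each set can be fixed before the draw and are 2:2 whichever set is chosen.

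**Conclusion.** On the text as written, the allocation rule does not deliver the restricted randomisation it names. It allows two allocations where thousands are available at almost no cost, and its smallest two-sided permutation p-value is 1.0. The primary analysis remains usable, with type I error near 5% on average, provided site effects are exchangeable between the two sets. That condition depends on how the sets were formed and is not guaranteed by the randomisation.

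The conclusion rests on reading step two as the only random act. If the split is itself drawn from many balanced splits, it reduces to a request to describe that draw. The documents do not support the claim that the trial's inference is invalid or its error rate inflated. This is a cheap improvement, to be made before sites are allocated.

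**What to change.** If the split is already to be drawn at random from many balanced splits, say so in 3.1 and 9.1.3 and give the number of splits and the balance criteria. Otherwise, replace the two steps with the following:

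1. Name the balancing variables in full and set a numeric limit for each.
2. Enumerate, or sample, the 10:10 allocations that meet the limits and fit the 2:2 recruitment blocks of 4.2. Forming the five blocks first gives at most 7,776 candidates.
3. Check that no pair of sites is always together or always apart in the accepted list.
4. Report the number accepted. At least 40 are needed for a two-sided permutation test at 0.05; relax the limits if there are fewer.
5. Have the statistician draw one accepted allocation at random and document the draw.
6. Keep the list and add a permutation test over it as a sensitivity analysis in 9.3.2.

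The cost is protocol wording and a short script, with no extra sites or residents. Balance may be slightly less exact than in a single best split.
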